There was no apparent influence of the prime-boost interval (28 days or 56 days) on the safety profiles of the vaccines. The 14-day prime-boost interval seemed to be associated with higher frequencies of solicited adverse events relative to the 28-day and 56-day prime-boost intervals; however, due to the open-label design of the 14-day regimen, knowledge of the treatment assignment may have biased subjects' reporting.

Both vaccination sequences tested (ie, Ad26.ZEBOV prime followed by MVA-BN-Filo boost and MVA-BN-Filo prime followed by Ad26.ZEBOV boost) were highly immunogenic and induced considerable humoral and cellular immune responses. Extending the interval between the prime and boost led to increased antibody responses (magnitude at a 56-day prime-boost interval was about 1.8 times higher than at a 28-day prime-boost interval), while the effect was less pronounced or the reverse for T cell responses. The induced immune responses were functional, as demonstrated by the neutralizing activity of the antibody responses in all subjects. The composition of induced T cell response was favorable, with a high percentage of

polyfunctional T cells, which generally are thought to play a role in immunological memory and effector functions.

VAC52150EBL1002 is a randomized, placebo-controlled, observer-blind study in healthy adults evaluating the safety, tolerability and immunogenicity of heterologous and homologous prime-boost regimens using MVA-BN-Filo and Ad26.ZEBOV administered in different doses, sequences and schedules: MVA-BN-Filo (1x10⁸ TCID₅₀) as prime followed by a Ad26.ZEBOV (5x10¹⁰ vp) as boost at 14, 28, or 56 days after prime; Ad26.ZEBOV (5x10¹⁰ vp) as prime followed by MVA-BN-Filo (1x10⁸ TCID₅₀) as boost at 28 days after prime; Ad26.ZEBOV (5x10¹⁰ vp) as prime followed by a high dose of MVA-BN-Filo (4.4x10⁸ TCID₅₀) as boost at 14 days after the prime; a high dose of Ad26.ZEBOV (1x10¹¹ vp) as prime followed by a high dose of MVA-BN-Filo (4.4x10⁸ TCID₅₀) as boost at 28 days after the prime. All planned 128 subjects of VAC52150EBL1002 have received a prime dose, and 126 subjects have received a boost dose (2 subjects were withdrawn). No vaccine-related serious adverse events have been reported and no safety issues have been identified to date.

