3. STUDY DESIGN AND RATIONALE

3.1. Overview of Study Design

This is a multi-country, prospective, long-term clinical safety study designed to extend the total follow-up period of vaccinated subjects up to 60 months (including the duration in the subject's original study), to allow collection of serious adverse events and pregnancy outcomes (including

spontaneous/elective abortion, intrauterine death/stillbirth, information on delivery) following administration of Ad26.ZEBOV and/or MVA-BN-Filo for the prevention of Ebola virus disease among subjects who participated in a Phase 1, 2 or 3 clinical study. In addition, offspring from vaccinated female subjects who became pregnant with estimated conception within 28 days after vaccination with MVA-BN-Filo or within 3 months after vaccination with Ad26.ZEBOV in a Phase 1, 2 or 3 clinical study will be followed up to 60 months after birth. Up to approximately 3,000 subjects may potentially be enrolled in this study, based on the number of exposed subjects in the contributing Phase 1, 2 or 3 clinical studies.

Since validated assays are not available yet to assess immune responses in the ongoing Phase 2 and 3 studies, unblinding of these studies has been delayed. Therefore, subjects in the ongoing Phase 2 and 3 studies who reach the last study visit will be approached to consent for enrollment into the VAC52150 Vaccine Development Roll-over study for long-term safety surveillance (for a total of up to 60 months after the prime vaccination). After unblinding of their original study only subjects who received Ad26.ZEBOV and/or MVA-BN-Filo will remain in this VAC52150 Vaccine Development Roll-over study for long-term safety surveillance. After unblinding, subjects who received placebo and have already been enrolled into the VAC52150 Vaccine Development Roll-over study will be discontinued from further participation in this roll-over study. This also applies to pregnant subjects who received placebo (ie, subjects enrolled in Cohort 2) or offspring from vaccinated female subjects who received placebo (ie, subjects enrolled in Cohort 3).

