4. TREATMENT ALLOCATION AND BLINDING

This section is not applicable, since no vaccine will be administered in the current study and subjects are already unblinded in their original Phase 1, 2 or 3 clinical study.

Unblinding of the ongoing Phase 2 and 3 studies has been delayed. Therefore, under Amendment 1, subjects who received placebo in their original Phase 2 or 3 study will also be approached for enrollment into the VAC52150 roll-over study before unblinding of their original study.

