10.2. Withdrawal From the Study

A subject may be withdrawn from data collection in this study for any of the following reasons:

- Withdrawal of consent
- Lost to follow-up
- Death

After unblinding of their original study, subjects who received placebo will be withdrawn from further participation. This also applies to pregnant subjects who received placebo (ie, subjects enrolled in Cohort 2) or offspring from vaccinated female subjects who received placebo (ie, subjects enrolled in Cohort 3).

Subjects who are subsequently enrolled as a subject in another non-sponsor clinical study do not need to be withdrawn from the study. It is accepted that data collection in this study may be restricted by confidentiality agreement terms and/or conditions of another concurrent clinical study.

When a subject withdraws before completing the study, the reason for withdrawal is to be documented in the CRF and in the source documents.

If a subject is lost to follow-up, every reasonable effort must be made by the study-site personnel to contact the subject and determine the reason for withdrawal. The measures taken to follow up must be documented. In the event that the status of the subject cannot be determined and the

subject is considered to be lost to follow-up, an end-of-study form for the individual subject will be completed and a specific date for the last observation will be provided.

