11.5. Safety Analyses

The verbatim terms used in the CRF by investigators to document serious adverse events will be coded using the Medical Dictionary for Regulatory Activities (MedDRA). All serious adverse events will be included in the analysis. For each serious adverse event, the percentage of subjects who experience at least 1 occurrence of the given event and the number of events per person-year (where applicable) with corresponding 2-sided 95% confidence intervals will be provided, for each cohort and by original randomization (active vaccine versus placebo). In addition, these analyses will be provided by age group for Cohort 1.

The incidence of pregnancy, incidence of pregnancy outcomes (including spontaneous/elective abortion, intrauterine death/stillbirth, information on delivery) and incidence of live-born children will be summarized by original randomization (active vaccine versus placebo). Only pregnancies with estimated conception within 28 days after vaccination with MVA-BN-Filo or within 3 months after vaccination with Ad26.ZEBOV, and live-born children from these pregnancies, will be included.

Results for subjects who received active vaccine or placebo will be presented separately.

A summary for subjects who die or who discontinue due to a serious adverse event will be provided.

The use of medications taken in relation to serious adverse events will be summarized.

Additional summaries, listings, datasets, or subject narratives may be provided, as appropriate.

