12.1.2. Attribution Definitions

Every effort should be made by the investigator to explain any adverse event and to assess its potential causal relationship, ie, to administration of the study vaccine or to alternative causes, eg, natural history of underlying disease(s), concomitant drug(s). This applies to all adverse events, whether serious or non-serious. Assessment of causality must be done by a licensed study physician (the investigator or designee).

The investigator will use the following guidelines to assess the causal relationship of an adverse event to study vaccine:

Not Related

An adverse event that is not related to the use of the study vaccine.

Doubtful

An adverse event for which an alternative explanation is more likely, eg, concomitant drug(s), concomitant disease(s), or the relationship in time suggests that a causal relationship is unlikely.

Possible

An adverse event that might be due to the use of the study vaccine. An alternative explanation, eg, concomitant drug(s), concomitant disease(s), is inconclusive. The relationship in time is reasonable; therefore, the causal relationship cannot be excluded.

Probable

An adverse event that might be due to the use of the study vaccine. The relationship in time is suggestive. An alternative explanation is less likely, eg, concomitant drug(s), concomitant disease(s).

Very Likely

An adverse event that is listed as a possible adverse reaction and cannot be reasonably explained by an alternative explanation, eg, concomitant drug(s), concomitant disease(s). The relationship in time is very suggestive.

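### Section 11.5 sets active and placebo SAE figures side by side although placebo follow-up stops at unblinding: the crude percentages are not comparable, and the person-year rates may not be

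*Protocol*

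**What the plan says.** Section 11.5 of the protocol fixes two statistics for each SAE: the percentage of subjects with at least one occurrence, and the number of events per person-year where applicable. Both come "with corresponding 2-sided 95% confidence intervals will be provided", "for each cohort and by original randomization (active vaccine versus placebo". The synopsis likewise plans incidence rates with intervals and separate presentation of active and placebo results. Neither place divides follow-up at unblinding.

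The design sections give the two groups different follow-up. Section 10.2 states: "After unblinding of their original study, subjects who received placebo will be withdrawn from further participation". Section 3.1 states the other half: "After unblinding of their original study only subjects who received Ad26.ZEBOV and/or MVA-BN-Filo will remain in this VAC52150 Vaccine Development Roll-over study". Section 10.2 extends the rule to placebo subjects in the pregnancy cohort and to the offspring of placebo recipients. Section 10.1 continues Cohort 1 data collection to 60 months after prime vaccination, counting the time in the original study.

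Section 4 says that "subjects are already unblinded in their original Phase 1, 2 or 3 clinical study", and in its next paragraph that unblinding of the ongoing Phase 2 and 3 studies has been delayed. The two statements need reconciling. As far as the first applies, those vaccinees contribute only open-label time to the roll-over.

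**The concern.** Two separate things make the active and placebo columns unlike each other.

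The first is length of follow-up. A percentage with at least one event grows with time at risk. If one column stops at unblinding and the other runs to month 60, the longer column shows the higher percentage whatever the vaccine does.

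The second is the condition of observation. By design, placebo roll-over time is collected while treatment is unknown. The vaccinee column pools such time with time in which everyone still in the study is known to have been vaccinated. Cohort 1 contacts after the first visit are six-monthly and preferably by phone, and the SAE definition in Section 12.1.1 includes a category that rests on medical judgment. Reporting could shift once treatment is known. Section 1.1 accepts this mechanism for an open-label regimen in a Phase 1 study, where "knowledge of the treatment assignment may have biased" what subjects reported.

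The placebo column is the only internal reference for the background SAE rate. The study is meant to inform benefit-risk assessment (Section 2.2), and accumulating data may go into health authority submissions (Section 11.7). Two adjacent columns with confidence intervals will be read as a comparison.

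**Working it through.** The protocol states no event rate, unblinding date, placebo share or power figure that could be reproduced. The check is therefore direct arithmetic over a range.

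**Inputs**
- From the protocol: vaccinee follow-up of 60 months after prime (10.1); placebo follow-up ending at unblinding (3.1, 10.2); all SAEs counted, related or not (9.2.2, 11.5).
- Assumed: unblinding month U; month E from which time is counted (0 for the whole period from prime, 12 for the roll-over alone if the original study lasted 12 months); a constant SAE rate λ, the same in both groups; full retention; ratio r of open-label to blinded ascertainment.

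**Percentage with at least one SAE, no vaccine effect, r = 1**

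Placebo: 1 − exp(−λ(U − E)/12). Active: 1 − exp(−λ(60 − E)/12).

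For λ = 0.02 per person-year, E = 12 and U = 24, placebo is 1 − exp(−0.02) = 1.98% and active is 1 − exp(−0.08) = 7.69%. The same formula gives:

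| Counted from | Unblinding at month | Placebo | Active | Ratio |
|---|---|---|---|---|
| month 12 | 24 | 1.98% | 7.69% | 3.88 |
| month 12 | 36 | 3.92% | 7.69% | 1.96 |
| month 12 | 48 | 5.82% | 7.69% | 1.32 |
| prime | 24 | 3.92% | 9.52% | 2.43 |
| prime | 36 | 5.82% | 9.52% | 1.63 |
| prime | 48 | 7.69% | 9.52% | 1.24 |

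The ratio depends little on λ. For E = 12 and U = 24 it is 3.94 at λ = 0.01 and 3.72 at λ = 0.05.

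**Events per person-year, no vaccine effect**

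Open-label share of vaccinee time: f = (60 − U)/(60 − E). Counted from prime, f is 0.80, 0.60, 0.40 and 0.20 for U = 12, 24, 36 and 48. Counted from month 12, f is 0.75, 0.50 and 0.25 for U = 24, 36 and 48. It exceeds one half only if U is below 30 (from prime) or below 36 (from month 12).

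Null rate ratio, active over placebo: (1 − f) + f·r.

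| Open-label share f | r = 0.8 | r = 1 | r = 1.25 |
|---|---|---|---|
| 0.25 | 0.95 | 1.00 | 1.06 |
| 0.50 | 0.90 | 1.00 | 1.13 |
| 0.75 | 0.85 | 1.00 | 1.19 |
| 1.00 | 0.80 | 1.00 | 1.25 |

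**With both columns stopped at unblinding**

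Then f = 0, so the null rate ratio is 1.00 for any r. Within an original study both groups are at risk for the same planned time, so the percentages also agree under no effect.

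**Price in precision**

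At a constant rate, the interval on the log-rate scale widens by about 1/√(share of active person-time kept). Counted from prime, the share kept is U/60:
- U = 36: 1/√0.60 = 1.3
- U = 24: 1/√0.40 = 1.6
- U = 12: 1/√0.20 = 2.2

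**The case against.** The best defence is that the protocol promises no comparison. It sets no hypothesis (2.2), plans no test (11.6), calls the study non-comparative (11.7) and says the two groups will be presented separately (11.5). Every endpoint in 11.1 concerns recipients of the study vaccines; placebo subjects entered only because unblinding was late. Section 11 leaves detail to the SAP, and 11.2 already warns of bias from observational data and loss to follow-up.

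Part of this stands: no test is invalidated, and the harm is to how descriptive figures are read. It does not remove the point. The protocol itself fixes the grouping and both statistics, and the warning in 11.2 does not name this asymmetry.

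A reader might also infer more than the text supports:
- **That the person-year rates must differ.** They differ only if r is not 1. No passage shows that, and the contact schedule and SAE criteria are the same for both groups while enrolled. The Section 1.1 remark concerned solicited events in one open-label regimen. It makes the mechanism plausible for SAEs but does not demonstrate it; deaths and hospitalizations leave less room for discretion.
- **That most vaccinee time is open-label.** This needs an unblinding date the protocol does not give. It is certain only for the roll-over time of vaccinees already unblinded at entry.
- **That open-label causality assessment distorts these tables.** It cannot, because 11.5 counts all SAEs and specifies no table of related ones.

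**Conclusion.** The point holds in two parts of different strength.

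The crude percentages by original randomization are not comparable. This follows from the follow-up rules alone and needs no assumption about reporting behaviour. Its size depends on the unblinding date and on when counting starts: with no vaccine effect, the active percentage is about 1.2 to 3.9 times the placebo percentage over the dates tabulated (months 24 to 48), at an assumed constant 0.02 SAE per person-year with full retention.

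The person-year rates correct for length of follow-up at a constant rate, but they may carry a difference in ascertainment. That is a possibility, of unknown size and direction. For an assumed r of 0.8 to 1.25, the null rate ratio lies between 0.95 and 1.06 at a 25% open-label share and between 0.85 and 1.19 at 75%.

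The full-period vaccinee rate is unaffected as a single-arm description. What fails is reading the placebo column beside it as a like-for-like background rate. This should be corrected, since the tabulation is stated in the protocol and the correction is small.

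**What to change.** In Section 11.5 and the synopsis:

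1. Limit the active-versus-placebo SAE tabulations, in both columns, to events and person-time accrued before the unblinding date of each subject's original study. Leave out open-label regimens, and the post-unblinding roll-over time of subjects whose study was already unblinded at entry.
2. Show vaccinees' post-unblinding and open-label events and person-time in a separate, uncontrolled active column with no placebo column beside it.
3. Keep the full 0 to 60 month rate in vaccinees as the single-arm endpoint of Section 11.1.

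The cost is a change of wording, one unblinding date per original study and one additional table split. The active column of the side-by-side table loses person-time. Its interval on the log-rate scale becomes about 1.3 times wider if unblinding is at month 36 and about 2.2 times wider if at month 12 (assumed dates, counted from prime). That loss is not trivial, but the time removed has no placebo counterpart. The 60-month single-arm estimate does not change.

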5.1. Inclusion Criteria

Each potential subject must satisfy all of the following criteria to be enrolled in the current study:

- 1. Criteria modified per amendment 1
- 1.1 Criterion modified per amendment 2
- 1.2 Male or female who participated in a Phase 1, 2 or 3 clinical study with Ad26.ZEBOV and/or MVA-BN-Filo and has been exposed to Ad26.ZEBOV and/or MVA-BN-Filo (or placebo) (Cohort 1);

or

Female who participated in a Phase 1, 2 or 3 clinical study with Ad26.ZEBOV and/or MVA-BN-Filo and became pregnant with estimated conception within 28 days after vaccination with MVA-BN-Filo (or placebo) or within 3 months after vaccination with Ad26.ZEBOV (or placebo) (Cohort 2);

or

Child born to a female subject exposed to Ad26.ZEBOV and/or MVA-BN-Filo (or placebo) in a Phase 1, 2, or 3 clinical study who became pregnant with estimated conception within 28 days after vaccination with MVA-BN-Filo (or placebo) or within 3 months after vaccination with Ad26.ZEBOV (or placebo) (Cohort 3).

Note: Each local authority will determine which cohorts will be opened for enrollment in their region. It is not mandatory to open all cohorts for enrollment. As a result, a local authority may restrict enrollment to 1 or 2 cohorts, rather than allowing enrollment in all cohorts.

2. Must sign an ICF for the current study (or their legally acceptable representative must sign) indicating that he or she understands the purpose of, and procedures required for, the study and is willing to participate in the study (or let their child participate).

Note: Assent is also required of children capable of understanding the nature of the study (typically 7 years of age and older) as described in Section 16.2.3.

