11.1. Endpoints

The following endpoints will be analyzed:

- Incidence of serious adverse events in subjects exposed to Ad26.ZEBOV and/or MVA-BN-Filo in a Phase 1, 2 or 3 clinical study, up to 60 months after prime vaccination.
- Incidence of pregnancy with estimated conception within 28 days after vaccination with MVA-BN-Filo or within 3 months after vaccination with Ad26.ZEBOV.
- Incidence of pregnancy by pregnancy outcome.
- Incidence of live-born children from a pregnancy with estimated conception within 28 days after vaccination with MVA-BN-Filo or within 3 months after vaccination with Ad26.ZEBOV.
- Incidence of serious adverse events in children born from a pregnancy with estimated conception within 28 days after vaccination with MVA-BN-Filo or within 3 months after vaccination with Ad26.ZEBOV up to 60 months after birth.

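### Section 11.5 tabulates pregnancies by active vaccine versus placebo, but its inclusion rule admits only conceptions after active vaccine, so the placebo column is zero by construction

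*Protocol*

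**What the plan says.** Protocol section 11.5 states that pregnancy incidence, pregnancy outcomes and live births "will be summarized by original randomization (active vaccine versus placebo". The following sentence sets the inclusion rule, which also governs the live-born children counted: "Only pregnancies with estimated conception within 28 days after vaccination with MVA-BN-Filo or within 3 months after vaccination with Ad26.ZEBOV". The next paragraph adds: "Results for subjects who received active vaccine or placebo will be presented separately".

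The corresponding endpoint in section 11.1 is likewise worded for active vaccine only: "Incidence of pregnancy with estimated conception within 28 days after vaccination with MVA-BN-Filo or within 3 months after vaccination with Ad26.ZEBOV". The live-birth endpoint there carries the same restriction.

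Eligibility for Cohort 2 in section 5.1 is wider. It takes in a woman who "became pregnant with estimated conception within 28 days after vaccination with MVA-BN-Filo (or placebo) or within 3 months after vaccination with Ad26.ZEBOV (or placebo". The placebo parenthesis also follows both windows in the Synopsis, the Time and Events Schedule for Cohorts 2 and 3, and sections 3.1, 9.2.2, 10.1 and 12.3.2.

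**The concern.** The study enrols placebo recipients who conceive, follows their pregnancies and children, and plans to show them in their own column. The analysis rule then removes them from that column, because the rule is tied to the two named products.

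Three stated endpoints are affected: pregnancy, pregnancy by outcome, and live births. The Synopsis plans incidence rates for pregnancy with two-sided 95% confidence intervals, so a programmer who follows the text would print a zero for placebo, possibly with an interval around it. A reader of the table could take that for the finding that no placebo recipient conceived in the window.

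A programmer who instead borrows the placebo wording from eligibility must decide which window a placebo dose carries. The protocol does not say. Section 9.2.1 dates exposure by the administration date and does not mention which vaccine a placebo dose stood in for.

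**Working it through.** The protocol gives no pregnancy count, precision or window-length figure, so there is no stated number to reproduce. The check has two parts.

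**1. The text, side by side**

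| Place | Placebo mentioned in the windows? |
|---|---|
| 5.1 eligibility; 9.2.2 data collection; also Synopsis, Time and Events Schedule, 3.1, 10.1, 12.3.2 | Yes, after each vaccine |
| 11.1 pregnancy and live-birth endpoints | No |
| 11.5 inclusion sentence | No |
| 11.5 tabulation | Active and placebo columns |

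Take a woman given placebo at both visits who conceives 20 days after the first. She qualifies for Cohort 2 under 5.1 and her outcome is recorded under 9.2.2. Under the 11.5 sentence she has no MVA-BN-Filo or Ad26.ZEBOV dose from which to date conception, so she is not counted. The same holds for every placebo-only recipient, so the placebo numerator is 0 whatever the data show.

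**2. What the missing wording could mean**

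Inputs: windows of 28 days (MVA-BN-Filo) and 3 months (Ad26.ZEBOV), from 5.1 and 11.5. Intervals of 14, 28 and 56 days come from the Phase 1 descriptions in section 1.1, and 84 days is the upper end of the 2 to 12 weeks given there for the programme. Assumptions: 3 months = 91 days, and both doses given on schedule.

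For windows w1 after the prime (day 0) and w2 after the boost (day g), the qualifying days are w1 + w2 if g ≥ w1, and max(w1, g + w2) otherwise.

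- Reading A: a placebo dose takes the window of the vaccine it replaced. Placebo and active days are then identical, ratio 1.00 in every regimen.
- Reading B: any placebo dose qualifies for 3 months, so w1 = w2 = 91 for placebo.

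Worked example, Ad26.ZEBOV first at 56 days: active max(91, 56 + 28) = 91; placebo under B max(91, 56 + 91) = 147; ratio 147/91 = 1.62.

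| Interval (days) | Placebo, reading B | Active, Ad26.ZEBOV first | Ratio | Active, MVA-BN-Filo first | Ratio |
|---|---|---|---|---|---|
| 14 | 105 | 91 | 1.15 | 105 | 1.00 |
| 28 | 119 | 91 | 1.31 | 119 | 1.00 |
| 56 | 147 | 91 | 1.62 | 119 | 1.24 |
| 84 | 175 | 112 | 1.56 | 119 | 1.47 |

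Taking 3 months as 90 or 92 days moves these ratios by at most about 0.02. Reading B peaks for Ad26.ZEBOV first at 63 days, (63 + 91)/91 = 1.69, but the protocol describes no regimen at that interval. Outside the heterologous regimens, reading B gives 1.00 for Ad26.ZEBOV twice, 2.1 to 3.1 for MVA-BN-Filo twice, and 91/28 = 3.25 for a woman with only one dose in an MVA-BN-Filo slot.

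**The case against.** The strongest reply is that this is an editorial slip. Section 11.5 names a placebo column and then requires separate placebo results, so the intention is plain and a sensible analyst would supply the missing words. A blank column would also be noticed. The active-only endpoints in 11.1 match the objectives in 2.1, which concern exposed subjects. The study is descriptive, section 11.7 calls it non-comparative, section 11.6 plans no formal testing, and placebo subjects are present only because unblinding was delayed. The statistical analysis plan, not shown here, may settle the detail.

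Much of this stands. There is no planned comparison to bias, only a side-by-side summary, and active-only wording in 11.1 is a problem only so far as those endpoints are reported by arm. The rest does not remove the point. The sentence in 11.5 is restrictive and names the products, whereas the protocol adds placebo to these windows in many other places. An analysis plan faithful to the sentence reproduces the zero, and one that departs from it must choose a placebo window that the protocol leaves undefined.

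A reader might go further and infer that the eligibility wording gives placebo recipients a longer window, so that pregnancy would look less frequent on vaccine: 91/147 = 0.62, or 38% lower, for Ad26.ZEBOV first at 56 days with equal conception rates. The document does not support that. The parenthesis is attached separately to each vaccine and its own window, which reads at least as naturally as the placebo given in that vaccine's place. If any placebo dose met the 3-month limb, the first parenthesis would be redundant. The 38% also needs a constant conception rate and full two-dose schedules, and the protocol gives no mix of regimens from which to form a programme-wide figure.

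**Conclusion.** The inclusion sentence in 11.5 is wrong as written. It contradicts the tabulation in the sentence before it, and it excludes placebo pregnancies and live births that the study enrols and records. Followed literally, the placebo entry is exactly zero for all three pregnancy summaries. This conclusion rests on the text alone and needs no numerical assumption.

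The length of the placebo window is a separate, lesser matter: an unresolved ambiguity. The placebo/active ratio of qualifying days is 1.00 if placebo doses are matched to the vaccine replaced, and 1.00 to about 1.6 in heterologous two-dose regimens at the four intervals calculated if they are not. No bias in either direction is shown.

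**What to change.** In the 11.5 inclusion sentence, add *or the placebo given in its place* after each vaccine, so that each placebo dose takes the window of the vaccine it replaced. Make the same addition to the pregnancy and live-birth endpoints in 11.1 so far as they are reported by arm. State that the assignment is made from the parent-study regimen after unblinding. Alternatively, drop the placebo column for the pregnancy summaries and say so.

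Leave the windows and the 5.1 eligibility criterion unchanged. Women may be enrolled before unblinding, when the vaccine a placebo dose replaced may not be known, so a rule based on it belongs in the analysis. Reporting pregnancies per person-time spent inside the window is optional.

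The cost is a few words in two sections, through the amendment route in 17.1. No new data collection is foreseen. The regimen sequence should be available from the parent studies, but this protocol does not describe the Phase 2 and 3 designs, so the sponsor should confirm it.
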